## **Inclusion/Exclusion Criteria**

### **Inclusion Criteria**

1. Male and female outpatients, age 18 years or older
2. Fluent in English
3. Have nonmalignant chronic musculoskeletal pain for more than 3 months
4. Able to perform a 6-minute walk test (6MWT)
5. Owns a smartphone with Bluetooth 4.0 or computer
6. Willingness and ability to participate in one of the 2 programs and to comply with the requirements of the study protocol.
7. Free of concurrent psychotropic medication for at least 2 weeks prior to initiation of treatment, OR stable on current medication for a minimum of 6 weeks and willing to maintain a stable dose

8. Low-level of activity (must meet 2/3 criteria; if difficult to assess, recruiter may ask participant to report their recent step data from their smartphone to better understand their activity level)
  - a. Sitting for more than 8 hours/day per self-report
  - b. Exercising for fewer than 3 days/week (30+min of exercise constitutes an “exercise day”) per self-report
  - c. Walking for fewer than 7 days/week (30+min of walking constitutes a “walking day”) per self-report

### **Exclusion Criteria**

1. Diagnosed with a medical illness expected to worsen in the next 6 months (e.g., malignancy)
2. Serious mental illness or instability for which hospitalization may be likely in the next 6 months
3. Current active suicidal ideation with plan or intent reported on self-report
4. Untreated and/or unstable schizophrenia, bipolar disorder, or other psychotic disorder
5. Current, active substance abuse or dependence, and current alcohol dependence within the past 6 months
6. Practice of yoga, meditation, guided imagery or other mind body techniques that elicit the RR, once per week for >45 min 3 times/week within the last 3 months or less.
7. Regular use of Fitbit DMD in the last 3 months
8. Unable to walk/in a wheelchair
9. Mild cognitive decline for participants 65+ only (Short Portable Mental Status Questionnaire; PMSQ 4 or more errors).

Participants will be adult patients with chronic, heterogeneous, non-malignant pain diagnosed by their medical provider. Participants will only include English speakers, due to study resources and access to translators. Participants who do not have access to a personal smartphone equipped with Bluetooth 4.0 or later may be provided with one. As in our feasibility R34 we anticipate that the majority of recruitment will occur from the Pain Clinics affiliated with each site, due to an overabundance of available study participants and due to the larger goal of implementation of programs within the Pain Clinic. Adults with chronic pain will be recruited from physician referrals and IRB approved flyers throughout all MGH, Duke, and Rush outpatient clinics and community health centers, social media, and from the community. In the event that a provider refers a patient without sharing contact information and the patient agrees to be contacted by the study team, the research assistant will use the patient’s medical record to access this information. Participants may also be recruited via referrals from related research studies, if they agree to be contact by our study team. In addition to the shared recruitment strategies, each site will have site-specific methods of recruitment. MGH will utilize the Mass General Brigham Rally platform to recruit patients from the greater Boston area. Duke University will also recruit via medical record review. Rush will also promote the study during the hospital “hold message” when people call Rush Medical Center. Screening will take place remotely and consent will occur in person.

### **5. Subject Enrollment**

The screening process will take place remotely and consent will occur in person. Remote screening will be conducted by the research assistant over the phone. During the screening call, a research assistant will provide study details to participants and assess eligibility via self-report questions. Participants will also have the option of completing a portion of this screening on their own via REDCap. There will be a QR code and link directing potential participants to the screening REDCap on our study flyers. If eligible after individual screening, the participant will receive a call from the research assistant. A research assistant will briefly review the consent form with eligible participants who express interest and intent to participate in the study. The research assistant will ask eligible participants to provide (1) their height and weight information, to initialize their ActiGraph, (2) dates and times that they are available to attend the group program and maintain a detailed log of this information. Study staff will continue to follow-up with interested participants via phone until a date for the groups has been selected (group times are based off a majority of participants' availability). Once a mutual date and time for the groups has been selected, a research assistant will call eligible participants to schedule an in-person group baseline assessment at each of the 3 sites, which includes the informed consent procedure. The research assistant will ask eligible participants who are not available at the set time if they want to be contacted for the next round of groups or for future trials. Though the timeline to hear back from the study team may vary, participants on the waiting list can expect to hear from us within a month and are guaranteed to be recontacted. Individuals who do not meet study criteria will be offered a resource sheet with relevant health and mental health information. During the in-person baseline assessment, participants will sign consent forms electronically on REDCap through the eConsent framework.

## **6. Study Procedures**

Eligible participants who are able to attend the scheduled group sessions will meet in person at each of the 3 sites for the baseline assessment. If other eligible participants are available at the same time, there is an option to conduct the baseline concurrently as a group. The baseline assessment includes: i) informed consent process through REDCap; ii) 6 minute walk test (6MWT) using a standardized protocol; iii) self-report questionnaires; iv) instructions on ActiGraph wear with special attention to explaining the importance of adherence and reducing reactivity (e.g., ensuring that participants know not to make changes in activity levels during the week long baseline assessment, and developing individualized plans for ActiGraph wear including option for Twilio text reminders). Participants will next be randomized to one of the 2 conditions. Allocation will be performed by each site study coordinator using REDCap. Each program involves audio-recorded group sessions (e.g., ~4-10 participants per group) for 10 consecutive weeks, 60 minutes per week at a time that is convenient to participants. Program sessions will be led by clinical psychologists who have undergone extensive training in these interventions and have expertise in chronic pain. Participants will also be invited to participate in a group exit interview following a semi-structured script. The group interview will occur during the post-intervention assessment. Those who are interested in participating but cannot attend the group interview session can participate individually at another time. All participants will also be given the opportunity to share contact information after the post-test assessments to maintain the community and relationships developed during the in-person group sessions.

The *GetActive-Fitbit* program is a group mind-body program developed iteratively from the Relaxation Response Resiliency Program (3RP) that incorporates additional cognitive behavioral and physical restoration skills (e.g., quota-based pacing) to help individuals increase self-reported, performance-based, and objectively measured (step count) physical function. Participants randomly assigned to this intervention condition will receive daily text/email reminders to practice program skills, record their walking, and record their skills practice via methods such as Twilio, if they consent to receive text reminders. A health education program (“Healthy Living for Pain”) will serve as the comparison condition for this aim of the study and will teach participants about health topics such as sleep, nutrition, and exercise. Participants randomly assigned to this comparison condition will receive journaling homework with daily text/email reminders. Participants will be given the option to share a copy of their journal with the study clinician throughout the program.

All participants will wear the ActiGraph wGT3X-BT devices to measure step-count at baseline, post-intervention, and 6-month follow-up assessments. All participants will be instructed on ActiGraph maintenance using standard operating procedures used in a prior feasibility trial at MGH. Participants will return the ActiGraph watches after the assessments, provided they have logged seven consecutive days of valid data. Participants with missing data will be instructed to continue wearing the device until seven days have been reached. The RA will provide participants with ActiGraphs either in-person or via mail, and participants will be asked to return their devices during in-person assessments, during sessions, or via mail with a prepaid postage envelope. The RA will remotely monitor ActiGraph adherence using CentrePoint Sync. For participants in the *GetActive-Fitbit* condition, participants will be asked to wear a Fitbit Inspire 3 for the duration of the program and sync the Fitbit to a Fitbit application on their smartphone. Using the Fitbit steps, the RA will determine a new step count goal weekly based on whether the *GetActive-Fitbit* participant met their step goal in the prior week. If a participant met their step-count goal, they will increase their steps by 10%. If they did not meet the goal, they will continue with the same goal. If they do not meet the goal for 2 consecutive weeks, their goal will be increased by 10% of the average step count they had accomplished the week prior. Study clinicians may also conduct independent check-ins with participants who do not meet their goal to ensure barriers are known. The standard baseline goal for all participants randomized to the *GetActive-Fitbit* condition is that they experience a 1,000 step increase by the end of the program, though this will be variable depending on participant ability.

The following measures will be administered at all timepoints, to participants in both study arms, unless otherwise stated. The measures assess physical and emotional function, behavior, medical symptoms, and coping strategies with pain. These measures will be administered on hospital-owned encrypted devices or paper and pencil, depending on participant comfort, and should take about 30 minutes to complete.

Demographics (baseline only)

Treatments (post-tests and follow-up only)

Pain, Enjoyment of Life and General Activity scale (PEG-3)

WHO Disability Assessment Scale (WHODAS)

6 Minute Walk Test (6MWT)

ActiGraph wGT3X-BT Accelerometer

PROMIS depression v1.08b

PROMIS anxiety v1.08a

Pain Catastrophizing Scale (PCS)

Tampa Kinesiophobia Scale (TSK)

Measure of Current Status (MOCS)

Cognitive and Affective Mindfulness Scale (CAMS)

Modified Global Impression of Change (MGIC) – only at post-test

Credibility/Expectancy Questionnaire (CEQ) (post-tests or as soon as possible after post-tests)

Client Satisfaction Questionnaire (CSQ-3) (post-tests or as soon as possible after post-tests)

Fitbit Use (GetActive Only)- only at 6-month follow-up

Table 1. Study Procedures		
Time	Task	Details
6-7 Weeks Before Intervention	Recruitment and Screening	RA receives referrals, screens via telephone, records availability for eligible participants
3 Weeks Before Intervention	Scheduling	RA selects baseline time based on participant availability. RA calls participants to confirm time.
~1 Week Before Intervention	Consent and Baseline Assessment	Review and sign consent. Participants complete: self-report measures, 6-minute walk test, Participants also receive ActiGraph devices and instructions.
10-Week Intervention	Group Sessions 1-10	Participants complete 10 weeks of group sessions of either GetActive-Fitbit or Healthy Living for Pain .  Sessions will be audio recorded, to ensure accuracy of delivery and assess fidelity.
1 Week Post Intervention	Post-Intervention Assessments	Participants repeat procedures from the baseline assessment. Participants return ActiGraph devices after the post-test assessment in person.
2 Weeks Before 6-Month Assessments	ActiGraphs Mailed Out	RA mails ActiGraphs to participants to be worn in week prior to 6-Month Follow up
6 Months Post Intervention	6-Month Follow-Up Assessments	Participants repeat procedures from the baseline and post-test assessments. Participants return ActiGraph devices after the 6-month follow-up assessment in person.

Participants will be paid \$945 for completing the study in its totality. If participants do not complete the study, we will pay based on the following study visits and tasks completed:

- For the baseline assessment, participants will receive \$60 for the completion of study tasks and up to \$100 additional dollars for ActiGraph wear (\$10 dollar per day, plus an additional \$30 for 7 days with complete valid wear).
- For the post-test assessment, participants will receive \$100 for the completion of study tasks and up to \$155 additional dollars for ActiGraph wear (\$15 dollar per day, plus an additional \$50 for 7 days with complete valid wear).
- For the 6-month follow-up assessment, participants will receive \$100 for the completion of study tasks and up to \$190 additional dollars for ActiGraph wear (\$20 dollar per day, plus an additional \$50 for 7 days).
- For transportation costs for session attendance, participants will be paid \$150 for travel compensation (\$15 per session) and can receive an additional \$50 if 8/10 sessions are attended.
- For the optional exit interview, participants will receive \$40.

Participants should expect to receive payment following each major assessment timepoint (i.e., baseline, post-test, and 6-month follow-up) as well as following the program sessions. MGH and Rush will pay participants via checks, as per their respective hospitals payment systems, and Duke will pay participants via ClinCards, per their hospital system.

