### **Statistical analyses:**

First, we will report:

- percent eligible sedentary chronic pain patients who enroll after being determined eligible during screening (benchmark  $\geq 80\%$  AND 34/90 racial and ethnic minorities).

- Total duration of recruitment in months overall and at each site.
- Percent of patients who attend  $\geq 7/10$  sessions for each program (benchmark is 80%).
- Percent patients with credibility scores higher than the scale's mid point (Credibility and Expectancy scale; benchmark is 80%)
- Percent patients with satisfaction scores higher than the scale's mid point (Client Satisfaction scale; benchmark is 80%)
- Percent patients who complete post-treatment (benchmark is 80%) and 6 months follow up (benchmark is 70%) including self-report, performance based and Actigraph valid data.
- Percent accuracy of standardized protocol checklists for all assessments (benchmark is 90% accuracy).
- We will also report additional information necessary to complete the CONSORT diagram.

Next, we will use Fisher's exact tests to make comparisons of number of people meeting each benchmark across sites and between the intervention arms, while also plotting performance metrics across sites to account and assess for trends in differences due to the low statistical power.

Estimates of variance components required for design of a future efficacy trial will be obtained from preliminary analysis of outcome report, performance based, and objective/ambulatory measurements in mixed model repeated-measures analyses.

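### Does the open-ended baseline ActiGraph wear rule put enough program days into the baseline step count to require a change?

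*Combined protocol and SAP*

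**What the plan says.** Table 1 in Section 6 places consent, the baseline assessment and the device hand-out at about "1 Week Before Intervention". Sections 3 and 6 describe baseline as lasting a week: staff are to make sure that participants do not "make changes in activity levels during the week long baseline assessment". Devices go back once seven consecutive valid days are logged, and the next sentence adds: "Participants with missing data will be instructed to continue wearing the device until seven days have been reached". Participants may "return their devices during in-person assessments, during sessions, or via mail".

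At 6 months, Table 1 names the wear week: "RA mails ActiGraphs to participants to be worn in week prior to 6-Month Follow up".

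GetActive-Fitbit participants are "asked to wear a Fitbit Inspire 3 for the duration of the program". The standard goal is that "they experience a 1,000 step increase by the end of the program".

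Section 9 (Statistical analyses) uses ActiGraph data in two ways. Valid data count toward the post-treatment and 6-month completion benchmarks. The step measurements also enter mixed models: "Estimates of variance components required for design of a future efficacy trial will be obtained from preliminary analysis". It does not say which recorded days make up the baseline value.

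**The concern.** Hand-out about seven days before session 1, with seven days required, leaves almost no slack. One invalid day pushes wear past session 1. From then on the arms are treated differently, because only one of them has a tracker and weekly step goals. If those days were averaged into baseline, the baseline would be partly a program measurement in one arm, and a later estimate of step change there would be too small. Return of devices during sessions shows that baseline devices may still be out when the program starts. In a trial that tested step change this would be a bias by arm, so the absence of a cut-off deserves a look.

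**Working it through.** **1. What the passages settle.** The week-long baseline, the hand-out about a week ahead and the payment for seven days (7 × $10 + $30 = $100) together place the intended window in the week before session 1. The extension sentence is a rule for returning devices at all three timepoints. It does not say that days after session 1 count as baseline. It adds days and removes none, and wear is monitored remotely and paid by the day, so earlier days stay identifiable.

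**2. How often wear could overrun.** The documents give no wear-adherence figure. Assume independent days, exactly seven wear days before session 1, and daily validity p = 0.98, 0.95, 0.90 or 0.80 (the last deliberately poor).

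- Share short of seven valid days at session 1: 1 − p^7.
- Mean late days if any seven valid days suffice (cumulative): 7 − 7p.
- Mean late days if the seven must be consecutive: by simulation. Expected total wear is (1 − p^7)/((1 − p)p^7) = 7.6, 8.6, 10.9 and 18.8 days.

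**3. How far the baseline would move.** The only program figure is 1,000 steps by program end. Assume a straight line over 70 days, so program day d adds 1,000/70 × d = 14.3d steps. With one invalid day, on wear day j, a consecutive run ends on day j + 7 and includes program days 1 to j. The shift is 14.3 × j(j + 1)/2 ÷ 7, which is 2 steps for j = 1 and 57 for j = 7. Simulating the whole process gives the last row below. For the cumulative reading, a generous flat 100 steps (1,000/10, the level at the end of week 1) is applied to each late day: mean late days ÷ 7 × 100.

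| Daily validity (assumed) | 0.98 | 0.95 | 0.90 | 0.80 |
|---|---|---|---|---|
| Short of seven days at session 1 | 13% | 30% | 52% | 79% |
| Mean late days, cumulative | 0.14 | 0.35 | 0.70 | 1.40 |
| Mean late days, consecutive | 0.56 | 1.37 | 2.65 | 4.66 |
| Shift in GetActive-Fitbit mean baseline, cumulative (steps/day) | 2 | 5 | 10 | 20 |
| Shift in GetActive-Fitbit mean baseline, consecutive (steps/day) | 4 | 13 | 37 | 137 |

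**4. Effect on the variance components.** In the worst cell (0.80, consecutive) the variance of the shift is about 34,000. Against an assumed between-person SD of 2,500 to 1,500 steps, that is 34,000/2,500² = 0.5% to 34,000/1,500² = 1.5%, if the shift is unrelated to a participant's true level.

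**5. What a cut-off would cost.** On the same assumptions, stopping at session 1 leaves the 13% to 79% in the first row short. Mean days kept are 7p = 6.9 to 5.6, and 0.03% to 15% of participants keep fewer than five. Five days in place of seven raises the variance of a participant's baseline mean by (ICC + (1 − ICC)/5)/(ICC + (1 − ICC)/7) − 1, which is 2% at a single-day ICC of 0.7 and 7% at 0.4 (both assumed).

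**The case for a change.** The best argument for acting is that a feasibility trial is the cheapest place to settle a measurement window. Aim 3 is to refine procedures for the efficacy trial, where baseline steps would matter more, and the wording would take one line. A length is not a closing date, and the instruction to hold activity steady sits badly with baseline days recorded inside a program meant to raise it. The plan also leaves open whether the seven days are consecutive or cumulative, and randomization may come before the wear week, so allocation could be known during it.

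Much of this stands as description. No cut-off is written, and the two sentences on seven days differ. It does not reach a planned result. Before session 1 neither arm is in the program, so early knowledge of allocation does not bring step goals with it. Return during sessions does not prove late wear: someone who finished on time could hand the device in at session 1. The 6-month row is a weak contrast, since it too names a week without a cut-off and falls under the same extension rule. Aim 3 already provides for refining procedures once this trial has shown how wear goes in practice.

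**Conclusion.** The gap exists, but it is a missing detail that analysts can fill sensibly. The intended week is clear, the earlier days are kept, and none of the planned benchmarks uses baseline steps. Section 9 plans no arm comparison of step change that a shifted baseline could distort.

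Even if late days were averaged in, the shift in one arm's mean baseline is about 2 to 20 steps a day on the cumulative reading and 4 to 137 on the consecutive reading. At worst it adds about 0.5% to 1.5% to the baseline variance. These sizes rest on assumed daily validity, independent days, exactly seven lead days and a straight-line response that meets the program goal in full. Wear plans, text reminders, remote monitoring and payment should push validity toward the better end. The true frequency of overrun cannot be read from the documents, and procedures not shown may already define the window.

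A strict cut-off would exchange this small bias for incomplete baseline weeks in an unknown share of participants. Either choice is defensible here, and neither alters what the trial can conclude about fidelity or feasibility.

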**Conceptual model:** We propose that intervention targets such as 1) nonadaptive reactions to nociception (kinesiophobia, and catastrophizing), 2) adaptive coping strategies (e.g., mindfulness, resiliency); 3)

social-emotional factors (depression, anxiety, social support, social isolation) will be interrelated and synergistically lead to improvement in physical function. Activity goal setting skills (pairing of step-count with activities of daily living depicted by patients as important, gradually increasing step goals via quota-based pacing, using the Fitbit live reinforcement of activity) are conceptualized as key factors in improving outcomes in *GetActive-Fitbit*. The program skills act by directly addressing habitual negative affective reactions to pain and negative pain thoughts by focusing on accepting and learning to tolerate pain sensations (including during increased activity), while Fitbit based on operant approaches previously depicted as promising in this population, acts by directly targeting increased activity through “quota-based” pacing and immediate feedback on number of steps achieved. In our conceptualization, the mind-body skills are necessary in order to bypass barriers to activity, and the Fitbit is necessary in order to maintain motivation and reinforce activity in real time.

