## 2. Specific Aims and Objectives

**Aim 1:** To test multisite fidelity of training and implementation of *GetActive-Fitbit* vs *HEP*, among adults with heterogeneous, non-malignant, musculoskeletal chronic pain.

**Hypothesis:** We hypothesize that study clinicians can be trained consistently and competently across sites to achieve implementation of the 2 programs with high adherence and competence based on a-priori set benchmarks.

**Aim 2:** To evaluate multisite feasibility benchmarks including ability to recruit sedentary chronic pain patients and racial and ethnic minorities for a protocol involving randomization to *GetActive-Fitbit* versus *HEP* with post-program and 6 months follow up.

**Hypothesis:** We hypothesize that we will meet a-priori set feasibility benchmarks including ability to recruit and retain racial and ethnic minorities through a 6-months follow-up (38% minorities).

**Aim 3:** To optimize our fidelity and study implementation protocol procedures in preparation for a future fully powered multisite efficacy RCT through the UH3/UG3 mechanism (PAR-21-243).

**Hypothesis:** We expect that we will successfully refine training, implementation and procedures using an iterative approach with separate focus groups with patients and staff, and within and cross-site meetings.

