All participants will wear the ActiGraph devices at the baseline, post-intervention, and 6-month follow up assessments. All participants will be instructed on ActiGraph maintenance using standard operating procedures used in a prior feasibility trial at MGH. Participants will return the ActiGraph watches after the assessments, provided they have logged seven consecutive days of valid data. Participants with missing data will be instructed to continue wearing the device until seven days have been reached. The RA will provide participants with ActiGraphs either in-person or via mail, and participants will be asked to return their devices during in-person assessments, during sessions, or via mail with a prepaid postage envelope. The RA will remotely monitor ActiGraph adherence using CentrePoint Sync. For participants in the *GetActive-Fitbit* condition, participants will be asked to wear a Fitbit for the duration of the program and sync the Fitbit to a Fitbit application on their smartphone. Using the Fitbit steps, the RA will determine a new step count goal weekly based on whether the *GetActive-Fitbit* participant met their step goal in the prior week. If a participant met their step-count goal, they will increase their steps by 10%. If they did not meet the goal, they will continue with the same goal. If they do not meet the goal for 2 consecutive weeks, their goal will be decreased by 10%.

Aim 3 will commence following Aim 2, and this aim of the study is intended to optimize fidelity and study implementation protocol procedures in preparation for a future fully powered multisite efficacy RCT. This aim will entail conducting focus groups with staff and patients to refine study materials and procedures. A future IRB submission will detail this aim in greater detail.

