## 7. Risks and Discomforts

Patients will be informed that the foreseeable physical risks from this research study are minimal. They will be informed that there is some risk of breach of privacy/confidentiality associated with the use of written communication (e.g., emailing, text messages) and audio recording software. They will also be informed of the unlikely situation that they might feel uncomfortable with the topics discussed within the group, and they can alert the group leader who will provide help, as needed. The group leaders are experienced clinical psychologists who have specific expertise with chronic pain in adults. They will also be informed that they may feel uncomfortable completing various psychological questionnaires and that they may find it time-consuming to participate in weekly 60-minute groups.

In the unlikely event that a participant is determined to be in distress or actively suicidal and at risk for self-harm during any study procedure, we will use a standardized protocol for assessing and monitoring risk developed by [name] that has been successfully used in other remote trials. In this protocol, the research assistant would contact the MPI ([name]) and the appropriate clinical intervention would be executed. In case we are unable to contact the participant we will contact their safety contacts (see Potential Risks to participant section). In case suicidality is determined during the intervention or control sessions, the study clinicians will perform safety procedures in real time and immediately contact the MPIs. Further, we set serious mental illness and current suicidal ideation as exclusion criteria to further reduce the chance that enrolled participants would express harm towards themselves or others at any point during the study.

Direct adverse events from increasing walking are not expected. The increase in activity will be safe, quota-based and gradual, contingent upon meeting step count criteria in the previous week. All study staff have been trained in responsible conduct of research. Adverse events during the study will be tracked as part of the daily adherence/home practice log. Specifically, participants will be asked if they experienced any negative outcomes because of becoming more physically active during that day. Any participants reporting adverse events will be immediately contacted and, if necessary, assessed by the study clinician before being referred for appropriate care as needed.

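### Sections 3 and 6 give conflicting rules for the weekly step goal after two missed weeks, and Section 6 as worded also conflicts with the Section 7 safety statement

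*Combined protocol and SAP*

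**What the plan says.** Sections 3 and 6 both describe how the research assistant sets the weekly Fitbit step goal. They share two of their three branches:

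- After a met goal, it rises by a tenth: "If a participant met their step-count goal, they will increase their steps by 10" percent (Section 3, with the same sentence in Section 6).
- After one missed week, it is unchanged: "If they did not meet the goal, they will continue with the same goal" (Section 6, with the same sentence in Section 3).

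They part at two consecutive missed weeks:

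- Section 3: "If they do not meet the goal for 2 consecutive weeks, their goal will be decreased by 10" percent.
- Section 6: "If they do not meet the goal for 2 consecutive weeks, their goal will be increased by 10% of the average step count" achieved in the prior week.

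Section 7 (Risks and Discomforts) then describes how activity will rise: "The increase in activity will be safe, quota-based and gradual, contingent upon meeting step count criteria in the previous week".

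Section 1 explains why the algorithm matters. In the conceptual model, "gradually increasing step goals via quota-based pacing, using the Fitbit live reinforcement of activity) are conceptualized as key factors in improving outcomes" for this arm.

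**The concern.** The same trigger leads to two different actions. Direction differs (down in Section 3, up in Section 6 as worded), and so does the base (current goal in Section 3, achieved average in Section 6). Neither passage is marked as superseded, and no order of precedence is given.

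Section 6 as worded also raises the goal because it was missed twice. Section 7 tells the reader that increases follow only when the previous week's criteria are met, so the risk description does not describe the procedure.

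The stakes concern delivery rather than inference. Research assistants at three sites could each follow the protocol and still give the same participant different goals. Section 10 has the principal investigators monitor adherence to the approved protocol, but on this step following one section means departing from the other. Aim 1 in Section 2 is "To test multisite fidelity of training and implementation of" the two programs, and Aim 3 is to refine procedures for a later efficacy trial, so an unresolved rule could carry forward.

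**Working it through.** There is no stated sample size, power or error rate to reproduce here. The check is a comparison of text, with arithmetic to show how far the rules diverge.

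**Inputs.** G is the current goal and A is the average achieved in the prior week. The 10% figures come from Sections 3 and 6. The documents give no typical goal or achieved average, so G = 4,000 and A from 2,000 to 3,800 are assumptions.

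**Rules after two consecutive missed weeks**

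- Section 3: new goal = 0.9 × G
- Section 6, literal: new goal = G + 0.1 × A
- Section 6, alternative reading (reset to 10% above what was achieved): new goal = 1.1 × A

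**Results for G = 4,000** (difference from Section 3 in brackets)

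| A | Section 3 | Section 6 literal | Section 6 as reset |
|---|---|---|---|
| 2,000 | 3,600 | 4,200 (+600) | 2,200 (−1,400) |
| 3,000 | 3,600 | 4,300 (+700) | 3,300 (−300) |
| 3,800 | 3,600 | 4,380 (+780) | 4,180 (+580) |

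**When can the sections agree?**

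- Literal reading: G + 0.1A = 0.9G would need a negative A, so they never agree. The goal rises whenever A > 0.
- Reset reading: 1.1A = 0.9G gives A/G = 0.9/1.1 = 0.818. With G = 4,000 that is A ≈ 3,273, the only point of agreement.

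**When does Section 6 conflict with Section 7?**

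- Literal reading: always, because a goal missed twice goes up.
- Reset reading: when 1.1A > G, that is A/G > 1/1.1 = 0.909. With G = 4,000 that is A above about 3,636.

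**Repeated misses.** Suppose the participant starts at 4,000, keeps averaging 3,000, and the two-week count restarts after each change (a further assumption).

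- Section 3 gives 3,600, then 3,240, then 4,000 × 0.9³ = 2,916 in week 7, now below the achieved average.
- Section 6 read literally adds 300 each time and reaches 4,000 + 4 × 300 = 5,200 by week 9.
- The reset reading stays at 3,300.

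For scale, Section 6 sets the usual whole-program target at an increase of 1,000 steps.

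**The case against.** The strongest reply is that Section 6 was probably not meant literally. Taken as a reset to 110% of achieved steps, it lowers the goal whenever the average is below about 90.9% of it, which is the same direction as Section 3. Section 7 is also a general risk statement rather than an algorithm. This has force: the Section 7 conflict is certain only on the literal reading and conditional on the other. It does not remove the conflict with Section 3, which remains on the reset reading except at one ratio. A delivery rule that needs this much interpretation is itself unclear.

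Other points limit the reach of the finding, and they stand:

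- Section 3 describes Aim 1 fidelity through clinician training, mock groups and knowledge assessment. Section 10's checklist covers session content. Nothing says that goal-setting by the research assistant is scored, so the link to Aim 1 is an inference.
- Study manuals and operating procedures are not part of these documents. They may contain one clear rule, and no actual divergence between sites has been shown.
- Only GetActive-Fitbit participants with two consecutive misses are affected, and the documents give no frequency for this.
- Optional clinician check-ins and daily adverse-event logging are unaffected.
- The documents do not say whether a goal is met on a weekly average or on daily attainment. The 81.8% and 90.9% thresholds assume that goal and average are on the same basis.

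None of this shows that the two sections agree.

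**Conclusion.** The concern holds. Sections 3 and 6 contradict each other on the goal after two missed weeks, under either reading of Section 6. The conflict with Section 7 is certain on the literal wording. On the reset reading it arises only when the achieved average exceeds about 90.9% of the goal.

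At an assumed goal of 4,000 and averages of 2,000 to 3,800, the literal reading puts the goal 600 to 780 steps above Section 3. The reset reading runs from 1,400 below to 580 above. These figures show direction and order of size; they do not estimate effect in the trial. The planned 120 participants, the feasibility benchmarks in Section 9 and the analyses do not depend on the rule, and no harm is claimed. It needs correcting because a core part of the intervention has no single written rule and the risk section does not describe the procedure as worded.

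**What to change.** Reconcile Sections 3, 6 and 7 so that all three express one rule for two consecutive missed weeks. The rule should state:

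- the direction of the change;
- the base to which the 10% applies (the prior goal or the achieved average);
- how a met goal is judged (weekly average or daily attainment);
- whether the two-week count restarts after a change.

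Carry the same text into the research assistants' step-goal procedure and the intervention fidelity materials. Which rule to adopt is for the investigators, and this review takes no position on it.

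The cost is a protocol wording amendment and a procedure update. No new data or participants are needed.
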